Additional posters (digital and in print) guided by the Social Norms Approach [32-34] will be distributed to high schools. *The 'perceptions and beliefs of what is "normal" behavior in the people close to us'* [32] has been identified as a key factor modifying drug use behavior among young adults. It has been shown that adolescents and young adults tend to overestimate drug use in their respective peer group and that these incorrect perceptions are predictive of higher rates of personal drug use [35-37]. Regarding alcohol use, these misperceptions can include both rates of peer alcohol use (*descriptive norms*) and the social acceptability of alcohol use (*injunctive norms*). Students tend to overestimate the frequency and quantity of alcohol consumption of their peers, as well as their peers' acceptability of heavy drinking. The students are then motivated to match their own alcohol consumption to what is an incorrect overestimated perception. Previous social norms interventions have been found to be effective in changing attitudes and knowledge about the norms of alcohol use, and some have been effective in changing behavior [32, 36]. Based on the social norm approach the aim of the posters is to correct misperceptions about the group norm and thereby decrease the social pressure to drink excessively on the individual student. The posters include descriptive and injunctive norms, tailored to each high school, based on the baseline survey.

Parental Components

The aim of the components is to empower parents to talk to their children about alcohol and reach an agreement on their drinking habits. The materials inform parents that their attitudes toward alcohol are associated with how much their children drink (even though their children are now older and have entered high school). Furthermore, the parents will be encouraged and receive guidance on how to discuss alcohol with their child and make agreements. The parental component consists of three separate elements.

- School meeting for parents

At the beginning of the school year, all schools must invite parents of 1st year high school students to a parent meeting, to inform them of the high school's alcohol policy. Parents are encouraged to support high school policies and discuss alcohol with their child.

[figure not shown]
-Parent leaflet

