Proportion of 1 st year high school students who feel included in the social community at school	Are you part of the social community at your school?	Binary	Yes, always or yes, sometimes vs. Occasionally or seldom or never
Proportion of 1 st year high school students who feel included in the social community at school among students who do not drink or have a low alcohol intake (25% lowest quantile in mean weekly alcohol consumption among 1 st year students at baseline).	Are you part of the social community at your school?	Binary	Yes, always or Yes, sometimes vs. Occasionally or seldom or never

Potential negative side effect

Weekly alcohol consumption	How many units of alcohol have you been drinking on each of the days during the last week?	Continuous	Units of alcohol
Consumption of drugs.	Have you ever tried to smoke marihuana, weed, or pot?	Binary	Yes/no
	Have you ever tried other drugs than marihuana?	Binary	Yes/no

Mediators (determinants)

A clear alcohol policy	Leader/coordinator questionnaire (questions will be developed)
Alcohol policy communicated to students and parents	Leader questionnaire/coordinator (questions will be developed)
Enforcement of the alcohol policy	Leader questionnaire/coordinator (questions will be developed)

	Student questionnaire: Is it your experience that... Alcohol is sold at most social events at my high school?		
More alcohol-free social events, than events were alcohol is sold	Leader questionnaire/coordinator (questions have not been developed)		
Proportion of 1 st year high school students who overestimate the alcohol use among their peers	At your high school: How many units of alcohol do you think other young people with the same gender and school year as you drank at the last high school party you attended?	Binary	Proportion who think more than average
	Proportion who overestimate the average of the secondary outcome "Mean alcohol intake at the school during last school party"		
Proportion of 1 st year high school students who have felt a social pressure to drink	How often have you experienced any of the situations described below? I have felt a pressure to drink more than I would like to.	Binary	Often or sometimes vs. seldom or never or I never attended a party or anything like that where alcohol was served

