Proportion of 1 st year high school students who feel they can have fun without drinking	To what degree do you agree in the following(..)- I can have fun at a party without drinking	Binary	Highly agree or agree vs. neither agree nor disagree or disagree or highly disagree
Proportion of 1 st year high school students who are familiar with the high schools' alcohol policy	Do you know if your high school has an alcohol policy?	binary	Yes, we do, and I know the content vs. Yes, we do but I do not know the content or No, we don't, or I do not know if my high school has an alcohol policy

Proportion of 1 st year high school students who talk to their parents about alcohol	Have you talked to your parents about your use of alcohol?	Binary	Yes, we talk about it regularly vs. Yes, we have talked about it once recently or Yes, we talked about it a long ago or No we have never talked about it.
Proportion of 1 st year high school students who have agreements with their parents on how much they can drink	Do you have agreements with your parents about your alcohol consumption?	Binary	Yes/no

Change in determinants (mediators)

Based on the program theory we expect to see a difference in a range of determinants of excessive drinking between intervention and control high schools, addressed by the multiple intervention components. On the high school level, we expect to find clearer alcohol policies at intervention school, that are communicated to students and parents, stronger enforcement of the alcohol policy, and more alcohol-free social events than events where alcohol is sold, as compared to control schools. At student level, we expect to see a larger proportion of students who feel they can have fun without drinking at intervention schools, compared to control school. Further we expect a smaller proportion who overestimate the alcohol use among their peers and a smaller proportion who have felt a social pressure to drink, at intervention schools as compared to control schools. Additionally, we expect a larger proportion of students who know the high schools' alcohol policy, talk to their parents about alcohol and have rules/agreements with their parents on how much they can drink, among students in intervention schools, as compared to control schools.

Changes in determinants will be evaluated in statistical mediation analysis based on student and leader/coordinator questionnaire.

Sample size calculation

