A blinded version of the data will be used for data analysis. Outcomes will be analyzed after the principle of intention-to-treat including all students in the arm to which they were allocated independently of whether they received (or completed) the intervention as planned. Intention-to-treat analysis will be supplemented by per protocol analysis based on the implementation of intervention components (both on school and individual level). Multi-level models will be used to account for the clustering of students in schools and school classes. General and generalized linear models will be used to study continuous and binary outcomes. If the model assumptions of the general linear model are not fulfilled, transformation of the outcome will be performed. All analyses will be adjusted for sex, parental education level, parental income and baseline level of the outcome, to increase precision. Differential effects of intervention by sex, parental educational level on the primary outcome will be investigated (explorative analyses). We hypothesize that boys may experience stronger intervention effects than girls due to higher initial level of binge drinking [43]. We had no hypotheses of the direction of socioeconomic differences in intervention effects, as previous research has been inconsistent in the direction of intervention effects [44, 45].

If the number of missing outcomes is larger than 10% and the results of the primary outcome is significant, a worst-case scenario will be performed for the primary and secondary outcomes as sensitivity analyses. The missing outcome values in the one group will be imputed with the mean value of the primary or secondary outcome of the other group and vice versa.

The primary outcome will be tested with significance level of 5%. Analyses of the pre-defined secondary outcomes will be analyzed with no p-value adjustment due to multiplicity and the interpretation of these results will be assessed in the light of multiple testing. This means that statistically significant effects will be

interpreted in the context of increased risk of type I error. No significance testing will be performed for the exploratory outcomes.

We will apply mediation analysis to test our program theory and hypothesized assumptions of changes in specific determinants will lead to change in the primary outcome.

Process evaluation

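### Coding the peer-norm mediator as yes/no above the average discards the size of the misperception; the signed difference in units would test the social-norms step with more sensitivity

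*Combined protocol and SAP*

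**What the plan says.** The mediator is a row of Table 1, under Mediators (determinants). The student is asked "How many units of alcohol do you think other young people with the same gender and school year as you drank" at the last party, so the answer is a number of units. The row is typed as binary and scored as "Proportion who think more than average". The same row ties the score to a reference: "Proportion who overestimate the average of the secondary outcome", namely "Mean alcohol intake at the school during last school party".

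The social norms campaign is meant to act on this variable. Its description says "The posters include descriptive and injunctive norms, tailored to each high school, based on the baseline survey". Under Change in determinants (mediators) the plan predicts the direction: "Further we expect a smaller proportion who overestimate the alcohol use among their peers". Under Planned statistical analysis it adds: "We will apply mediation analysis to test our program theory".

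Table 1, the determinants text and the analysis section give no margin, no rounding rule and no continuous version of this variable. They also do not say whether the average is taken by school, sex or arm, or at which time point.

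**The concern.** The posters are supposed to bring students' beliefs closer to the true norm. This is the only row in Table 1 that measures misperceived peer drinking, so it carries the plan's test of that step. The questionnaire collects how far each student is from the norm, but the code records only which side of a line the student is on. Most of a real correction can take place above the line and go unseen. If so, the arm comparison and the mediation model could show little or nothing for the social-norms step when beliefs had in fact moved.

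**Working it through.** The documents give no figure for this mediator, so there is none to reproduce. They also give no mean, spread or bias for students' guesses. Every SD, bias and reference value below is an assumption.

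**1. What the code keeps.** Let d = guess − reference. The mediator is 1 if d > 0 and 0 otherwise. A student who moves from d = +8 to d = +1 scores 1 both times. With whole-unit guesses, SD 2 and a reference of 7.4, halving the mean overestimate from 8 to 4 units moves the proportion from about 100% to 97%. Halving it again, from 4 to 2, moves it to 83%.

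**2. Level when there is no misperception.** Take guesses centred on the reference r and rounded to whole units. The share coded as overestimating is 1 − Φ((floor(r) + 0.5 − r)/SD).

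| Reference | SD 2 | SD 3 | SD 4 |
|---|---|---|---|
| 7.4 | 48% | 49% | 49% |
| 7.6 | 52% | 51% | 51% |
| 8.0 | 40% | 43% | 45% |

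With SD 1 to 3 and other decimal parts of the average, whole-unit guesses give 31–66%. Poisson guesses give 35–49%, and right-skewed gamma guesses 37–48%.

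**3. Loss of sensitivity.** Assume normal guesses with mean bias b₁ in control schools and b₂ in intervention schools, and a common SD. Per student in each arm, the squared signal-to-noise ratio is:

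- continuous: (b₁ − b₂)² / (2·SD²)
- binary: (p₁ − p₂)² / [p₁(1 − p₁) + p₂(1 − p₂)], with p = Φ(b/SD)

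Relative efficiency is binary divided by continuous.

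- From +2 to +1, SD 4: p₁ = 0.691, p₂ = 0.599. Binary = 0.0928² / (0.2133 + 0.2403) = 0.0190. Continuous = 1/32 = 0.0313. Ratio 0.61.
- From +4 to +2, SD 2: p₁ = 0.977, p₂ = 0.841. Binary = 0.1359² / (0.0222 + 0.1335) = 0.1186. Continuous = 4/8 = 0.5. Ratio 0.24.

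These ratios treat students as independent. Clustering and covariate adjustment would change them somewhat.

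**4. Direction.** Take whole-unit guesses, with controls at +2 and SD 4.

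| Intervention schools | Reference 7.4 | Reference 7.6 |
|---|---|---|
| Mean bias falls to +1 | 68% → 59% | 70% → 61% |
| Mean bias falls to 0 | 68% → 49% | 70% → 51% |
| 30% repeat the reference rounded to a whole number | 68% → 48% | 70% → 79% |

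Ordinary shifts move the proportion the right way at both references. Only the last row reverses, and only when the average rounds up: 0.7 × 70% + 0.3 × 100% = 79%.

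**The case against.** A guess above the average is literally an overestimate, so the code measures what its name says and nobody is miscounted. The hypothesis is a contrast between arms and both arms use the same rule, so a non-zero level among unbiased guessers does not by itself bias the contrast. The row is one of several mediators and not a primary or secondary outcome. The raw units are collected, so a continuous version stays available. All of this stands. It limits the stakes, but does not restore the sensitivity lost by dichotomising, and an unplanned continuous analysis would carry less weight than a stated one.

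A reader might also infer that the proportion cannot fall much below one half, or that the posters will make it rise. The documents support neither. If students repeat the rounded figure and the reference is 7.4, the proportion in the scenario of step 4 is 27% when 60% do so and 0% when all do. The rise at 7.6 needs posters that show this average as a whole number, students who repeat it exactly, and scoring against an unrounded average that matches the poster figure. The plan says only that the posters carry school-tailored norms from the baseline survey.

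A further objection is that the same row has another fault: students guess what peers "drank at the last high school party you attended", while the reference is intake at the school during the party. That is a separate point, and the levels in steps 2 and 4 apply only if item and reference match. Matching them would leave the loss from the yes/no code in place.

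**Conclusion.** The point holds as a matter of sensitivity. The yes/no code discards the size of the misperception that the posters are meant to reduce. Under the assumed normal guesses it keeps about 60% of the continuous version's efficiency in the modest-shift example and about 25% in the example with larger overestimation. The proportion can also stay well above zero when guesses are right on average but noisy. These figures rest on assumed spreads and biases; that the code keeps only the sign follows from Table 1 itself. A reversed result is a special case and not a property of the plan. The consequence is confined to the arm comparison on this determinant and to the mediation analysis, so this is a worthwhile, low-cost improvement and no threat to the trial's main result.

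**What to change.** In Table 1, make the main form of this mediator continuous: perceived peer units minus the reference average, signed. Use it for the arm comparison and in the mediation model. State in advance how extreme answers are handled, by a cap or a robust method. Keep the proportion above the average as a descriptive figure only. Define the reference in the same edit (by school, sex and time point, and whether rounded), since both forms depend on it.

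A tolerance margin on the proportion is not a substitute. The documents give no basis for choosing one, and with a 1-unit margin and normal guesses 31% of unbiased guessers at SD 2, and 37% at SD 3, would still be coded as overestimating.

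The cost is one table row and a sentence in the analysis section. The question and the data stay the same. A mean difference in units is slightly harder to communicate than a proportion, and extreme answers need a rule.

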A checklist for high schools' development/revision of the alcohol policy was developed with the aim to limit availability of alcohol, help enforcement and communicate clear attitudes to alcohol. The checklist was based on evidence from the national alcohol policies [30, 31] that have shown effect previously and interviews with principals to ensure feasibility. Most initiatives were mandatory to implement; however, some initiatives were optional because of implementation challenges or weaker evidence of impact. Headmasters will receive the checklist and be asked to tick the initiatives they intend to introduce before the new 1st year high school students begin in August 2019. Each school can decide for itself whether they also want to introduce the optional items in the checklist. Headmasters are asked to sign the adapted checklist and return it to the Danish Cancer Society to be published on the project's website. In this way, the checklist can also become a tool for leaders to promote and label their high school as a responsible institution. Headmasters are responsible for implementing and enforcing the new policy.

School educational components

-Web based education for social student committees that organize events where alcohol is sold such as parties, cafés, concerts etc. were developed, alongside with an web-based educational program for the introduction committee welcoming 1st year high school students to the high school.

The purpose of the web-based educational programs to the social student committees and intro committees is to make students aware of their responsibility for developing inclusive events, were students that do not drink also feel welcome, and the fact that they act as role models for their peers. The programs will provide information on national legislation on alcohol at high schools, marketing of alcohol, school alcohol policy, information on drinking peer pressures and social norms for adolescent alcohol use. Further, the programs provide guidance to arrange appealing social events without focusing on alcohol.

Pocket movie campaign

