The primary outcome is mean number of binge drinking occasions within the last 30 days. 1st year high school students will be asked "*how many times within the last 30 days have you been drinking 5 or more units of alcohol within one occasion?*". Secondary outcomes are 1) mean weekly alcohol consumption, 2) mean alcohol intake at last school party, 3) mean alcohol intake at the school during

last school party, and 4) proportion of students who think alcohol plays a too dominant part at the school (see Table 1).

Explorative outcomes: a potential positive side effect of the intervention is that a higher proportion of students feels included in the social community at school. We want to look at this among all students and further do a stratified analysis among students who do not drink or have a low alcohol intake (25% lowest quantile in mean weekly alcohol consumption at baseline among students in both interventions and control group). A potential negative side effect of the intervention is a higher alcohol intake among students in the intervention group as a response to increased focus on alcohol, making it more interesting among students in intervention group. We will also study substitute effects by analyzing whether students in the intervention group are more likely to experiment with drugs as compared to students in the control group.

Table 1: Outcomes and mediators

Variable	Question	Type	Units/categories
Primary outcome			
Binge drinking occasions	How many times within the last 30 days have you been drinking 5 or more units of alcohol within one occasion?	Continuous	Occurrences
Secondary outcomes			
Weekly alcohol consumption	How many units of alcohol have you been drinking on each day during the last week?	Continuous	Units of alcohol
Alcohol intake at last school party	How many units of alcohol did you drink at the last high school party you attended?	Continuous	Units of alcohol
Alcohol intake at the school during last school party	How many units of alcohol did you drink at the school during high school party you attended?	Continuous	Units of alcohol
Proportion of 1 st year high school students who think alcohol play a too dominant part at the school	Do you feel that alcohol plays a too dominant part at your high school (e.g.	Binary	Yes/no

*at high school parties, school bars,
introduction trips, study tours etc.)?*

Explorative outcomes

Potential positive side effects

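### The peer-overestimation mediator asks about drinking at the last school party but is scored against the mean drunk at the school only

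*Combined protocol and SAP*

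**What the plan says.** Table 1 (Outcomes and mediators) keeps two party-intake measures apart. Secondary outcome 2 asks "How many units of alcohol did you drink at the last high school party you attended". Secondary outcome 3 is "alcohol intake at the school during last school party", and its question underlines the words for the school, so respondents are meant to notice the difference.

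The mediator row on overestimating peers asks how many units "you think other young people with the same gender and school year as you drank at the last high school party you attended". The question opens with a phrase naming the student's own high school. The row then scores the answer as above or below the average of the secondary outcome "Mean alcohol intake at the school during last school party". It does not say whether that average is taken per school, per arm or overall, or from which survey.

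The section on change in determinants expects "a smaller proportion who overestimate the alcohol use among their peers" at intervention schools, and the variable enters the mediation analysis. The social norms campaign section gives the rationale: "Students tend to overestimate the frequency and quantity of alcohol consumption of their peers".

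**The concern.** The question and its cut-off appear to refer to different quantities. On its more natural reading the item covers everything peers drank in connection with the party. The cut-off covers only what was drunk on the premises. If the two differ, a student whose guess is exactly right lies above the cut-off and is recorded as misperceiving.

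This variable is the direct check on whether the social norms posters corrected perceptions. An inflated proportion would misdescribe how common misperception is. A proportion pushed towards 100% also leaves less information for comparing the arms.

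**Working it through.** **Wording, side by side.**

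- Outcome 2: own intake at the last high school party attended, with no limit of place.
- Outcome 3: own intake at the school during the party, with the place underlined.
- Mediator item: peers' intake, ending in the same words as outcome 2 and without outcome 3's limit of place.
- Mediator cut-off: the mean of outcome 3, by name.

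No other section gives a different cut-off or explains this one. The plan states no figure for this variable, so there is none to reproduce.

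**Illustration. All inputs are assumed; the documents give none of them.** True mean total intake is 8 units. Guesses are normal with SD 3 or 4, centred at c. The at-school share is s. Then

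proportion flagged = P(guess > 8s) = 1 − Φ((8s − c)/SD).

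Example: c = 8, s = 0.7, SD 3. The cut-off is 5.6, (5.6 − 8)/3 = −0.80, and 78.8% are flagged although guesses are unbiased. The change column is for a real fall of 1 unit in perceived intake (c replaced by c − 1). Entries are SD 3 / SD 4.

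| s | c = 8: flagged % | change, points | c = 10: flagged % | change, points |
|---|---|---|---|---|
| 100% (matched) | 50.0 / 50.0 | −13.1 / −9.9 | 74.8 / 69.1 | −11.7 / −9.3 |
| 90% | 60.5 / 57.9 | −13.2 / −9.9 | 82.5 / 75.8 | −9.9 / −8.4 |
| 70% | 78.8 / 72.6 | −10.9 / −8.9 | 92.9 / 86.4 | −5.7 / −6.2 |
| 50% | 90.9 / 84.1 | −6.7 / −6.8 | 97.7 / 93.3 | −2.5 / −3.9 |
| 30% | 96.9 / 91.9 | −3.2 / −4.4 | 99.4 / 97.1 | −0.8 / −2.1 |

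**The same 1-unit fall on the odds-ratio scale (SD 3).**

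- c = 8: 0.59, 0.57 and 0.53 at s = 100%, 70% and 50%.
- c = 10: 0.58, 0.52 and 0.46.

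The odds ratio does not move towards 1.

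**Precision.** Take the unadjusted standardised contrast, (p₀ − p₁)/√[p₀(1 − p₀) + p₁(1 − p₁)], where p₀ and p₁ are the proportions flagged before and after the fall.

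- c = 10, SD 3: 0.180 matched, 0.136 at s = 70% (a loss of about a quarter), 0.096 at s = 50%.
- c = 10, SD 4: 0.138 matched, 0.118 at s = 70% (about 14% less).

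**Conditional between-arm case.** Suppose the average is school-specific at follow-up, and the at-school share is 70% in control schools and 60% in intervention schools, with total intake and perceptions equal. The cut-offs are 5.6 and 4.8.

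- c = 8: flagged 78.8% against 85.7% (SD 3), 72.6% against 78.8% (SD 4).
- c = 10: 92.9% against 95.8% (SD 3), 86.4% against 90.3% (SD 4).

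This is 3.0 to 6.9 points more apparent overestimation in the intervention arm, opposite to the expected direction.

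**Wave of the average, with outcome 2 as cut-off.** Let intake fall 20%, from 8 to 6.4 units, with perceptions initially centred on the truth.

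- Follow-up average, perceptions unchanged: 70.3 / 65.5% flagged, against 50%.
- 2019 average kept fixed, perceptions following intake down: 29.7 / 34.5% flagged, against 50%, although no misperception was corrected.

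**The case against.** **The item may already match its cut-off.** The opening phrase naming the student's high school could be read as a place. The documents also never say that outcome 2 includes off-premises drinking; that is inferred from the separate listing. This stands as a real ambiguity. But the phrase more naturally identifies whose drinking is meant, and outcome 3 shows how the plan words a limit of place when it wants one. On the other reading the item still needs rewording.

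**A reader might infer that the intervention effect on this mediator is attenuated.** That holds in percentage points only. The planned statistical analysis uses generalized linear models for binary outcomes without naming a link. With a logit link the illustration shows no attenuation. The loss is of precision, and it is smaller than the points suggest.

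**A reader might infer that the mismatch is what makes most students overestimators.** If students do overestimate, as the social norms section says, 69-75% are flagged in the illustration even with the matched cut-off.

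**A reader might infer a built-in bias between arms.** The alcohol policy checklist was developed "with the aim to limit availability of alcohol", so at-school intake could fall at intervention schools. But the bias needs a school- or arm-specific average taken at follow-up, and an at-school share that changes differently by arm. No section states either. With one pooled cut-off this artefact disappears. Moving to outcome 2 does not settle the choice of average: the shift of 15.5 to 20.3 points from a follow-up outcome 2 average exceeds the 3 to 7 points shown for outcome 3.

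**Stakes are low, and the answer in units can be rescored.** Both are true. Rescoring after the data are seen is still a weaker position than a correct rule set beforehand.

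**Conclusion.** The mismatch is in the current text. On the more natural reading of the item, the stated rule is wrong for the question asked, rather than merely short of detail. Whenever some party drinking is off the premises, accurate guesses are coded as overestimates, the reported proportion is too high, and the between-arm contrast loses precision.

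The size cannot be derived from the documents. The consequence is small if most drinking is at school: at a 90% share with unbiased guesses, the contrast in the illustration is unchanged, although the proportion flagged still rises by 8 to 10 points. It is substantial at shares near 50%. A between-arm bias is possible only under the conditions above and should not be claimed as a feature of the plan.

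The scope is one of ten mediator rows and its part in the mediation analysis. The primary and secondary outcomes, the sample size and the type I error are unaffected. The correction is worth making because it is specific and nearly free. Confidence is medium, given the second reading of the item.

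**What to change.** In the Table 1 row, name the mean of secondary outcome 2 as the cut-off, calculated for the peer group in the item (same school, sex and school year). This changes one row and needs no new data, since outcome 2 is already collected. The analysis section gives no scoring rule for mediators, so no other text changes.

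If at-school drinking was meant, reword the item to say so and keep outcome 3. The cost is that the item would differ from any baseline version already collected in January to March 2019.

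In either case, state the level and survey wave of the average before follow-up data are seen. Each wave has a cost. A follow-up average moves with actual drinking. The early 2019 average comes from first-year students surveyed before the intake for which schools choose policy items "before the new 1st year high school students begin in August 2019", and it can count a fall in drinking as corrected perception. Perceived units could be added as a continuous supplementary mediator; this is optional.

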Based on results from the Unplugged program [42], we expect a 30% lower mean number of binge drinking occasions within the last 30 days in the intervention group as compared to the control group at follow-up. Sample size calculation to estimate the number of high schools needed to recruit was performed using the

statistical software STATA v15 using *Sampsii* and *Sampclus*. The average number of binge-drinking episodes within the last 30 days was estimated based on data from the Danish National Youth Study 2014 [41]. In 2014, high school students had an average of 2.94 binge drinking occasions within the last 30 days, with a standard deviation of 2.58, an interclass correlation of 0.034, and an average of 198 enrolled 1st year students per high school (cluster size). Conventional levels of statistical power (0.8) and level of significance (0.05) were used. Under the above assumptions, calculations showed that at least 12 high schools should be recruited for the study to show a 30% reduction in the number of binge-drinking episodes within the last 30 days (6 control schools and 6 intervention school, equivalent to a total of 2,296 students). Due to the risk of loss to follow-up, we aimed at recruiting an additional 30%, corresponding to 16 high schools.

Planned statistical analysis

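### The floor of 12 schools for 80% power ignores the small number of schools: a t reference on 10 degrees of freedom gives 77%, though the 16 schools recruited still give about 90%

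*Combined protocol and SAP*

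**What the plan says.** The section "Sample size calculation" takes its effect from an earlier school programme: "we expect a 30% lower mean number of binge drinking occasions within the last 30 days in the intervention group". Its inputs come from a 2014 national survey: a mean of 2.94 episodes per 30 days, "with a standard deviation of 2.58, an interclass correlation of 0.034", and 198 first-year students per school. On error rates it says "Conventional levels of statistical power (0.8) and level of significance (0.05) were used". It names two Stata routines, one for the individual-level sample size and one for the cluster inflation.

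The result is that "calculations showed that at least 12 high schools should be recruited for the study to show a 30% reduction", given as 6 schools per arm and 2,296 students. For loss to follow-up, "we aimed at recruiting an additional 30%, corresponding to 16 high schools". The section does not say whether that loss is of schools or of students.

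The section "Planned statistical analysis" says "Multi-level models will be used to account for the clustering of students in schools and school classes". It sets the primary test at the 5% level and names no degrees-of-freedom or small-sample method. The effect evaluation section reports that 16 schools agreed to take part, allocated 1:1.

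**The concern.** Schools are randomized, so the error term for the treatment effect is the variation between schools. With 12 schools in two arms that variance is estimated on about 10 degrees of freedom, and a test that holds its 5% level needs a critical value of 2.228, not 1.96. If 1.96 is used with 10 degrees of freedom, the actual type I error is P(|t| > 1.96) = 7.8%. The plan's formula uses normal quantiles throughout, so its power belongs to a test that does not keep the stated level.

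The 12 also serves as the floor beneath the loss allowance: 12 x 1.3 = 15.6, rounded up to 16. A team relying on this section would conclude that four whole schools could withdraw with 80% power intact.

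**Working it through.** **Inputs (sample size section).** Control mean 2.94; reduction 0.30 x 2.94 = 0.882; SD 2.58; intraclass correlation 0.034; 198 students per school; alpha 0.05; power 0.80. Sidedness is not stated. Two-sided is assumed, because a one-sided test needs about 1,632 students (8.2 schools) and does not reproduce 12.

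**Reproducing the plan's figure.**
- Individual level: n per arm = 2 x 2.58² x (1.960 + 0.842)² / 0.882² = 134.3, rounded up to 135.
- Design effect: 1 + 197 x 0.034 = 7.698.
- Per arm: 135 x 7.698 = 1,039.2, rounded up to 1,040, so 2,080 students in total.
- Schools per arm: 1,039.2 / 198 = 5.25, rounded up to 6, so 12 schools. The plan's 12 is reproduced.

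The 2,296 students are not reproduced by an exact 30% reduction. They are matched exactly by a difference of 0.84 (intervention mean 2.1, a 28.6% reduction): 149 x 7.698 = 1,147.002, rounded up to 1,148 per arm, or 2,296 in total. This also gives 12 schools (5.79 per arm). That 0.84 was used is an inference from the arithmetic; the plan does not say so.

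**Power with a t reference.**
- Variance of a school mean: 2.58² x 7.698 / 198 = 0.2588.
- SE of the difference with a and b schools: sqrt(0.2588 x (1/a + 1/b)).
- Non-centrality = difference / SE; degrees of freedom = a + b - 2.
- For 6+6: SE = 0.2937; non-centrality = 0.882 / 0.2937 = 3.003; 10 degrees of freedom.

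| Schools (by arm) | Normal, 0.882 | t, 0.882 | t, 0.84 |
|---|---|---|---|
| 16 (8/8) | 93.4% | 89.6% | 86.6% |
| 14 (7/7) | 90.0% | 84.5% | 80.9% |
| 14 (6/8) | 89.4% | 83.8% | 80.1% |
| 13 (6/7) | 87.6% | 80.9% | 77.1% |
| 13 (5/8) | 86.0% | 79% | 75.1% |
| 12 (6/6) | 85.2% | 77.2% | 73.2% |

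**Loss of whole schools.** From 16, losing two schools leaves at least 80% power however the loss falls between arms, at either difference. Losing three keeps 80% only at 0.882 and only if the split is 6/7. Losing four, two per arm, leaves 77.2%.

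**Loss of students.** If 30% of students are lost in each of 16 schools (0.7 x 198 = 138.6 left per school), t-based power is 88.1% at 0.882 and 84.9% at 0.84.

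**The case against.** A reader might infer that the plan contains an arithmetic error. The documents do not support that: the named method, applied to the stated inputs, returns 12 schools, at 85% by its own reckoning. The weakness is that a large-sample formula was used for few clusters, and the shortfall appears only with a degrees-of-freedom correction that the plan does not mention. That correction is not an arbitrary import, however. The plan commits to a 5% test, and with 12 schools a normal reference does not deliver one.

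A reader might also infer that the trial is underpowered. It is not, on these inputs: 16 schools were planned and 16 agreed, giving about 90% on the stricter basis.

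The loss argument bites only if whole schools withdraw. The plan says just loss to follow-up, and its missing-data rule concerns missing outcome values. If the 30% means students, the cushion is ample. Against that, the allowance is expressed in schools.

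Finally, the planned adjustment for baseline outcome, sex, parental education and parental income could recover the missing 3 points. The plan gives no size for the gain. As an assumption, cutting the variance of the difference by 5%, 7%, 10% or 20% lifts t-based power at 12 schools to 79%, 80%, 81% or 86%. A school-level covariate would also cost a degree of freedom (9 degrees of freedom: 76%). So 12 might suffice for the adjusted analysis, but the stated calculation neither claims nor shows that.

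**Conclusion.** The point holds, in a limited form. The stated floor of 12 schools gives 77%, not 80%, at a genuine two-sided 5% level without covariate gain, and 73% if the difference behind the 2,296 students was 0.84. The balanced minimum is 14 schools (85%, or 81% at 0.84).

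It would be tempting to say that three of the 16 schools can safely be lost. The plan's figures do not bear that out: a 5/8 split falls just below 80%, and at 0.84 even 6/7 gives 77%. The safe loss is two.

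The figures assume equal school sizes of 198 and the 2014 survey's SD and intraclass correlation. The consequence is modest, because the recruited number is adequate.

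**What to change.** In the sample size section:
- Give t-based power of 90% at 8+8, 85% at 7+7 and 77% at 6+6 schools, and say that the test is two-sided if that is intended.
- Give the balanced minimum as 14 schools, noting that 13 suffices only if split 6/7. State the tolerable loss as two of 16 schools, or three only with that split.
- Say whether the 30% allowance is for schools or for students.
- Reconcile the 2,296 students with the 2,080 that an exact 30% reduction gives. If 0.84 was the difference used, state it and use the matching power figures (87%, 81% and 73%).

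In the analysis section, name a small-sample degrees-of-freedom method for the multi-level model of the primary outcome, for example Kenward-Roger.

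The cost is a recalculation and some wording. No further schools or data are needed. The only downside is a slightly less favourable stated figure.
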